Appendix 16 Daily Subject Diary (For Artificial Tear Use)

If subjects are using artificial tears, they will be asked to complete a dosing diary for each administration. The dosing diary will collect the following information with respect to artificial tear administration:

Date	Time	Time	Time	Time	Time	Initials
DD/MMM/YYYY	HR/MIN	HR/MIN	HR/MIN	HR/MIN	HR/MIN	
//	AM/PM	AM/PM	AM/PM	AM/PM	AM/PM	

Due du et Merree	Commons	Indication	Decier	Marketed since
Product Name	Company	Indication	Kegion	Marketed since
Cequa [™] (0.9 mg/ml)	Sun Ophthalmics	DED (KCS with presumed suppression of tear production)	US	2018
Restasis [®] (0.5 mg/ml)	Allergan	DED (KCS with presumed suppression of tear production)	US, Canada, and 33 other countries	2003
Ikervis [®] (1.0 mg/ml)	Santen Pharmaceutical	DED (Severe keratitis which has not improved with tear substitutes)	Europe	2015
Papilock Mini [®] (1.0 mg/ml)	Santen Pharmaceutical	VKC	Japan	2005
Modusik-A Ofteno [®] (1.0 mg/ml)	Laboratorios Sophia	KCS with a functional decrease of lacrimal glands	Mexico, Chile Columbia, Peru, Ecuador, Argentina	2003
TJ Cyporin [®] (0.5 mg/ml)	Taejoon Pharma Co, Ltd	Ocular inflammation associated with KCS	South Korea	2003
Lacrinmune [®] (0.5 mg/ml)	Bausch & Lomb, Inc.	KCS with a functional decrease of lacrimal glands	Argentina	NA
Cyporin [®] (0.5 mg/ml)	Aristopharma, Ltd	Ocular inflammation associated with KCS	Bangladesh, Myanmar	NA
Cyclorin [®] (0.5 mg/ml)	Ibn Sina Pharmaceutical Industry, Ltd.	Ocular inflammation associated with KCS	Bangladesh	NA

Appendix 17	Marketed	Cyclosporine
-------------	----------	--------------

Adapted from Lallemand et al., 2017

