2. STUDY DESIGN

2.1. Synopsis of Study Design

This is a randomized, multi-center, double-masked, vehicle-controlled, phase 1/2 clinical study designed to evaluate the safety, tolerability, and efficacy of OTX-CSI (cyclosporine ophthalmic insert) for intracanalicular use for the treatment of subjects with DED. Approximately 145 subjects (290 eyes) will be enrolled in this study at approximately 15 sites in the US.

Subjects will be enrolled in two cohorts. Cohort 1 will be an open-label group consisting of approximately 5 subjects. Cohort 2 will be a randomized, double-masked group consisting of approximately 140 subjects treated with 2 different hydrogel formulations of OTX-CSI and 2 different formulations of hydrogel vehicle inserts (HV). Both eyes will be treated with the same treatment/formulation.

Cohort Number	Number of Subjects	Treatment	Formulation
1 Open-label	5	OTX-CSI	2A
2 Randomized, double-masked	40	OTX-CSI	1
	40	OTX-CSI	2A
	40	HV	2B
	20	HV	3

Cohort 1

Subjects in Cohort 1 will undergo Screening 14 days prior to Insertion/Day 1 (Visit 2) to determine eligibility and eligibility will be re-confirmed at Visit 2 (Insertion/Day 1). The treatment follow-up visits will occur at Week 2 (Visit 3), Week 4 (Visit 4), Week 6 (Visit 5), Week 9 (Visit 6), Week 12 (Visit 7), and Week 16 (Visit 8). All subjects in Cohort 1 will be followed until Week 16 (Visit 8) whether or not an insert is visualized.

Cohort 2

Subjects in Cohort 2 will undergo Screening 14 days prior to Insertion/Day 1 (Visit 2) to determine eligibility. At Visit 2 (Insertion/Day 1) eligibility will be confirmed and subjects who are eligible will be randomly assigned to one of four treatment groups (OTX-CSI Formulation 1, OTX-CSI Formulation 2A, HV Formulation 2B or HV Formulation 3) in a 2:2:2:1 ratio. Should only a unilateral insertion be possible, Visit 2B will occur within 3 days to attempt the insertion again. The treatment follow-up visits will occur at Week 2 (Visit 3), Week 4 (Visit 4), Week 6 (Visit 5),

Sponsor:	Ocular Therapeutix, Inc.			
Protocol:	CLN-Protocol-0054			
Document Version No.:	V1.0	Document Date:	01-OCT-2021	

Week 9 (Visit 6), Week 12 (Visit 7), and Week 16 (Visit 8). All subjects in Cohort 2 will be followed until Week 16 (Visit 8) whether or not an insert is visualized.

[figure not shown]

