2.6.2. Safety Variables

The safety variables are as follows:

- 1- Ocular and non-ocular adverse events
- 2- Best Corrected Visual Acuity (BCVA): LogMAR Visual Acuity (VA) score at each visit and its CFB at each post-baseline visit
- 3- Slit-Lamp biomicroscopy parameters by location (Eyelid Vascularity (vascular engorgement), Vascular, Engorgement of Eyelid Margin of upper and lower lid, Punctal Appearance, Lid Apposition, Lashes, Conjunctiva, Sclera, Cornea, Anterior Chamber, Iris, Pupil, Lens) by visit
- 4- Intraocular Pressure (IOP) measurement (mmHg) and its CFB by visit
- 5- Fundus Examination: Vitreous, Retina, Macula, Choroid, Optic nerve by visit
- 6- Artificial tears use during the study: the use of Artificial tears since last visit at each postbaseline visit.

Sponsor:	Ocular Therapeutix, Inc.			
Protocol:	CLN-Protocol-0054			
Document Version No.:	V1.0 Document Date: 01-OCT-2021			

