4.2.10. Visit Windows

Visit windows will be calculated based on the schedule of assessments in Table 1. Any visits or procedures performed outside the scheduled visits must be documented in the Unscheduled Visit page of the eCRF. Although there is a visit window around the expected visit date, nominal visits will be used for the per-visit analyses.

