LogMAR Visual Acuity (VA) score for each visit, its CFB, and loss of 3 Lines or more in BCVA LogMAR Score from Baseline at each post-baseline visit will be calculated and summarized using descriptive statistics.

2- Slit-Lamp biomicroscopy

The evaluation of normal, mild, moderate, severe, and very severe for each eye in Eyelid Vascularity (vascular engorgement) and Vascular Engorgement of Eyelid Margin of upper and lower lid, as well as normal, abnormal non-clinically significant, and abnormal clinically significant for each eye in Punctal Appearance, Lid Apposition, Lashes, Conjunctiva, Sclera, Cornea, Anterior Chamber, Iris, Pupil, and Lens will be tabulated for each visit by using the frequency and percentage.

3- Intraocular Pressure (IOP) measurement (mmHg)

Absolute value at baseline and visit 8 (week 16), its CFB, absolute IOP measurement \geq 30 mmHg at each visit, and CFB in IOP > 5 mmHg as well as >10 mmHg at Visit 8 will be summarized using descriptive statistics.

4- Fundus Examination

The evaluation of normal, abnormal non-clinically significant, and abnormal clinically significant for each eye in vitreous, retina, macula, choroid, and optic nerve exam will be tabulated for visit 1 and visit 8 by using the frequency and percentage. The absolute cup-to-disc ratio at baseline and Visit 8 (Week 16) and its CFB at Visit 8 (Week 16) will be presented using descriptive statistics.

5- Artificial tears use during the study

The use of artificial tears, based on the Daily Subject Diary, since last visit will be tabulated for each post-baseline visit by using frequency and percentage. Number of times AT used since last visit will be reported among all subjects who have any daily subject dairy data since the last visit using descriptive statistics.

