Document Version No.:	V1.0	Document Date:	01-OCT-2021

- Table 14.3.4.2 Non-Ocular Treatment-Emergent Adverse Events (TEAEs) Related to IP by System Organ Class and Preferred Term – SAFETY
- Table 14.3.4.3: Ocular Serious Treatment-Emergent Adverse Events (TEAEs) Related to IP by System Organ Class and Preferred Term – SAFETY
- Table 14.3.4.4: Non-Ocular Serious Treatment-Emergent Adverse Events (TEAEs) Related to IP by System Organ Class and Preferred Term – SAFETY
- Table 14.3.5.1: Maximum Severity of Ocular Treatment-Emergent Adverse Events (TEAEs) by System Organ Class and Preferred Term – SAFETY
- Table 14.3.5.2: Maximum Severity of Non-Ocular Treatment-Emergent Adverse Events (TEAEs) by System Organ Class and Preferred Term – SAFETY
- Table 14.3.6.1: Summary of Best Corrected Visual Acuity (BCVA) LogMAR VA Score and Change from Baseline on Study Eye by Visit SAFETY
- Table 14.3.6.2: Summary of Best Corrected Visual Acuity (BCVA) LogMAR VA Score and Change from Baseline on Non-Study Eye by Visit SAFETY
- Table 14.3.7.1: Summary of Intraocular Pressure (IOP) (mmHg), IOP ≥ 30 mmHg and Change from Baseline (CFB), CFB IOP >5 mmHg and >10 mmHg on Study Eye by Visit – SAFETY
- Table 14.3.7.2: Summary of Intraocular Pressure (IOP) (mmHg), IOP ≥ 30 mmHg and Change from Baseline (CFB), CFB IOP >5 mmHg and >10 mmHg on Non-Study Eye by Visit – SAFETY
- Table 14.3.8.1: Summary of Slit-Lamp Biomicroscopy Results on Study Eye by Location and Visit SAFETY
- Table 14.3.8.2: Summary of Slit-Lamp Biomicroscopy Results on Non-Study Eye by Location and Visit SAFETY
- Table 14.3.9.1: Summary of Fundus Examination Results on Study Eye by Visit SAFETY
- Table 14.3.9.2: Summary of Fundus Examination Results on Non-Study Eye by Visit SAFETY

Table 14.3.10: Summary of Artificial Tear Use from Baseline by Visit – SAFETY

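### Artificial-tear counts are reported per visit interval rather than per day, so steady use can look as if it rises when the gaps lengthen from 14 to 21 to 28 days

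*SAP*

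**What the plan says.** SAP 2.6.2 defines the safety variable as "Artificial tears use during the study: the use of Artificial tears since last visit at each postbaseline visit". SAP 4.9 item 5 then plans two summaries for each post-baseline visit:

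- Use of AT, as a categorical summary: "since last visit will be tabulated for each post-baseline visit by using frequency and percentage".
- A count, with descriptive statistics: "Number of times AT used since last visit will be reported among all subjects who have any daily subject dairy data since the last visit".

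The listed output is "Table 14.3.10: Summary of Artificial Tear Use from Baseline by Visit", on the Safety population. Its title speaks of baseline while the text speaks of the last visit. I take the text to govern.

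SAP 2.1 places the follow-up visits at Weeks 2, 4, 6, 9, 12 and 16. SAP 4.2.10 adds that "nominal visits will be used for the per-visit analyses". Neither document converts AT use to a daily or weekly rate, or adjusts for the length of the interval.

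On who supplies data, Protocol Appendix 16 says: "If subjects are using artificial tears, they will be asked to complete a dosing diary for each administration". Neither document says whether a subject without diary entries counts as zero uses or drops out of the denominator.

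**The concern.** A count over an interval depends on both the rate of use and the length of the interval. Here the interval lengthens by design after Week 6, so a table of counts by visit mixes the two.

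The timing is awkward. Protocol 4.2 and SAP 1.1 describe Formulation 1 as lasting about 2 to 3 months and Formulations 2A and 2B about 3 to 4 months. The longer gaps, ending at Weeks 9, 12 and 16, cover the period in which those inserts are designed to dissolve. A rise produced by the calendar could be read as waning effect. Conversely, a real fall in daily use of one third (Weeks 9 and 12) or one half (Week 16) would appear as a flat count.

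AT use is a listed secondary safety evaluation (Protocol 6.2.1), and tears remain available as needed throughout (Protocol 8.2), so the table is likely to be read for a time course.

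**Working it through.** The documents give no figure for AT use, so there is none to reproduce. The rates below are assumptions, chosen to span sparse to daily use.

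**Inputs.** Visit weeks 0, 2, 4, 6, 9, 12, 16 (SAP 2.1). Windows of ±2 days at Weeks 2 and 4 and ±3 days from Week 6 to Week 16 (SAP Table 1).

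**Nominal intervals.** 7 × (difference in weeks) = 14, 14, 14, 21, 21, 28 days. Against 14 days, 21/14 − 1 = +50% and 28/14 − 1 = +100%.

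**Formulas**, for an interval of d days:

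- Mean count over all subjects = rate × d.
- Percentage with any use = 1 − (1 − p)^d for a daily chance p with at most one use a day, or 1 − exp(−rate × d) for Poisson use.
- Mean count among users only = (rate × d) ÷ (proportion with any use).

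**Results** for 14, 21 and 28 days, with the change at 21 and 28 days against 14 days in brackets:

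| Assumed constant use | Any use | Mean count, all subjects | Mean count, users only |
|---|---|---|---|
| 2% daily chance | 25%, 35%, 43% (+40%, +75%) | 0.28, 0.42, 0.56 (+50%, +100%) | 1.14, 1.21, 1.30 (+7%, +14%) |
| 5% daily chance | 51%, 66%, 76% (+29%, +49%) | 0.70, 1.05, 1.40 (+50%, +100%) | 1.37, 1.59, 1.84 (+17%, +34%) |
| 0.5 uses/day, Poisson | 99.9%, 100%, 100% (about 0) | 7.0, 10.5, 14.0 (+50%, +100%) | 7.01, 10.5, 14.0 (+50%, +100%) |
| Exactly 1 use every day | 100%, 100%, 100% (0) | 14, 21, 28 (+50%, +100%) | 14, 21, 28 (+50%, +100%) |

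Worked line for 5%: 1 − 0.95^14 = 0.512, 1 − 0.95^21 = 0.659, 1 − 0.95^28 = 0.762. Users only: 0.70/0.512 = 1.37, 1.05/0.659 = 1.59, 1.40/0.762 = 1.84.

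So the 50% and 100% steps are exact for the count over all subjects at any constant rate. They shrink for sparse use if non-users are left out, and they do not apply to the any-use percentage.

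**Spread within one visit.** Taking the windows at both ends, the interval can run from 9 to 19 days at Week 6 (14 ± 5), 15 to 27 at Weeks 9 and 12 (21 ± 6), and 22 to 34 at Week 16 (28 ± 6). If the last visit means the last one attended, a subject who misses Week 9 brings 84 − 42 = 42 days to Week 12.

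**After dividing by days.** At one use per day, 14/14 = 21/21 = 28/28 = 1.0 at every visit, so the artefact disappears.

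**The case against.** The strongest reply is that no conclusion of the trial depends on this table. It is descriptive and no trend test on AT use is planned. All randomised arms share one schedule, so at any given visit the nominal interval is the same for each arm. The only AT threshold used in an analysis, the 60-drop rule for the per-protocol population (SAP 3.1), refers to the single interval from Week 9 to Week 12. Columns are labelled by visit, so a careful reader can see the gaps, and the same artefact would appear in the vehicle arms. Diary entries are dated and Listing 16.1.21 is planned, so a rate could be derived later. All of this stands, and it is why the point is minor.

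The reply does not remove the defect. A by-visit table invites reading across visits, and nothing planned shows the reader a rate. The protection for same-visit comparisons also assumes attendance on schedule. Subjects who terminate early complete the Visit 8 assessments (SAP 4.2.8), so intervals of unusual length can enter that visit. If missed visits or withdrawals differ by arm, interval lengths will differ too.

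A reader might infer more than the documents support:

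- **That every arm will show rising use.** Not so. An arm with little or no use shows little or nothing, and Protocol 8.2 discourages AT. The percentage does not rise for daily users.
- **That the artefact continues at the 30-day visit.** The documents disagree. Protocol 8.3.10 and Appendix 1 collect the diary at Visit 9. SAP Table 1 does not, and SAP 5 gives the SAP precedence. I leave that visit out.

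**Conclusion.** The point holds for the count of uses read across visits. With all subjects counted and a constant rate, the mean rises by 50% at Weeks 9 and 12 and by 100% at Week 16. If only users have diary data, the rise runs from about 7% and 14% (2% daily chance) to nearly the full 50% and 100% (from about 0.5 uses per day). The any-use percentage rises by less than the full-count mean, and by nothing for daily users. These ranges rest on the assumed rates and on constant use. The interval lengths come from the schedule.

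It would be wrong to infer that the treatment comparison is biased. With visits attended on schedule it is not, and no test or population definition is touched. Severity is minor, and the change is worth making because it costs little.

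**What to change.** In SAP 4.9 item 5 and Table 14.3.10:

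1. Add uses per day (or per 7 days) for each subject: number of uses divided by that subject's actual days since the last attended visit. Summarise it by treatment group and visit alongside the raw count.
2. State whether subjects without diary entries, and days without entries, count as zero. The rate cannot be defined without this rule, and it also settles the denominator of the existing count.
3. Print the nominal interval length under each visit heading. The any-use percentage can then stay as planned, with its changing time base visible.

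The cost is one derived variable, one rule for missing diary entries and a few words in the table shell. Visit dates and dated diary entries are already collected, so no new data are needed.

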4.9.1. Laboratory Data

Safety laboratory tests will not be collected. Urine pregnancy test results will be captured at Visit 1 and Visit 8 (Week 16). Urine pregnancy test results will be provided in data listing.

CRS-BS-TP-000005 V 1.0

Sponsor:	Ocular Therapeutix, Inc.		
Protocol:	CLN-Protocol-0054		
Document Version No.:	V1.0 Document Date: 01-OCT-2021		

4.9.2. Vital Signs and Physical Examinations

Vital signs and physical examinations data will not be collected.

4.9.3. **Concomitant Medications**

Concomitant medications will be coded using the WHO Drug dictionary, WHO DD B3 WHO Drug DDE – Sep 2019. Results will be tabulated by Anatomic Therapeutic Class (ATC) and preferred term.

Concomitant medications will be defined as those medications that were initiated after study drug administration or those that were ongoing at the time of study drug administration. If the start date or stop date of a medication is partially missing, the date will be compared as far as possible with the date of the start of administration of study drug. The medication will be assumed to be prior medication if it cannot be definitively shown that the medication did not start or continue during the treatment period.

Non-ocular prior and concomitant medications will be summarized by higher ATC level 3 (therapeutic subgroup) and preferred term by treatment group and overall, in the Safety population. ATC Level 3 terms will be sorted alphabetically. Preferred terms will be sorted by descending frequency overall within ATC Level 3 term. Subjects receiving a particular medication or medication of ATC Level 3 will be counted once at the preferred term level and once at ATC Level 3.

Ocular prior and concomitant medications will be summarized at the eye level, separately for study and non-study eyes, and at the subject level (both eyes) by ATC Level 3 and preferred term by treatment group and overall, in the Safety population.

All prior and concomitant medications information will be presented in the data listing.

Sponsor:	Ocular Therapeutix, Inc.		
Protocol:	CLN-Protocol-0054		
Document Version No.:	V1.0 Document Date: 01-OCT-2021		

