4.2.9. Missing, Unused, and Spurious Data

If the start date of an AE is partially or completely missing, the date will be compared as far as possible with the date of the start of administration of study drug. The AE will be assumed to be treatment-emergent if it cannot be definitively shown that the AE did not occur or worsen during the treatment-emergent period (worst case approach). The imputed dates will only be used to classify events as treatment emergent and will only be used in the table analyses. Listings will display the available date data.

The following general rules will be used:

- If the start day is missing but the start month and year are complete, an AE will only be excluded as being treatment-emergent if the start month/year is before the month/year of study drug administration or if the date of resolution is before study drug administration.
- If the start day and month are missing but the start year is complete, an AE will only be excluded as being treatment-emergent if start year is before the year of study drug administration or if the date of resolution is before study drug administration.
- If the start date is completely missing, an AE will be considered treatment-emergent unless the date of resolution is before study drug administration.

Sponsor:	Ocular Therape	Ocular Therapeutix, Inc.			
Protocol:	CLN-Protocol-0054				
Document Version No.:	V1.0	V1.0 Document Date: 01-OCT-2021			

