7. CLINICAL STUDY REPORT APPENDICES

7.1. Statistical Tables to be Generated

- Table 14.1.1: Overall Disposition and Subject Accountability All Subjects Screened
- Table 14.1.2: Overview of Analysis Sets
- Table 14.1.3: Major Protocol Deviations mITT and Cohort 1
- Table 14.1.4: Demographic and Baseline Characteristics mITT and Cohort 1
- Table 14.1.5: Ocular Characteristics at baseline mITT and Cohort 1
- Table 14.1.6.1: Study Eye Ocular Medical History mITT and Cohort 1
- Table 14.1.6.2: Non-Study Eye Ocular Medical History mITT and Cohort 1
- Table 14.1.6.3: Non-ocular Medical History mITT and Cohort 1
- Table 14.1.7.1: Study Eye Ocular Prior Medications SAFETY
- Table 14.1.7.2: Non-Study Eye Ocular Prior Medications SAFETY
- Table 14.1.7.3: Non-ocular Prior Medications SAFETY
- Table 14.1.7.4: Study Eye Ocular Concomitant Medications SAFETY
- Table 14.1.7.5: Non-Study Eye Ocular Concomitant Medications SAFETY
- Table 14.1.7.6: Non-ocular Concomitant Medications SAFETY
- Table 14.1.8: Treatment Exposure SAFETY
- Table 14.2.1.1.1: The Summary and Linear Model with MCMC Multiple Imputation of Change from Baseline in Schirmer Test (mm) on Study Eye at Visit 7 (Week 12) and other Post-Baseline Visits mITT
- Table 14.2.1.1.2: The Summary and Linear Model with MCMC Multiple Imputation of Change from Baseline in Schirmer Test (mm) on Study Eye at Visit 7 (Week 12) and other Post-Baseline Visits PP
- Table 14.2.1.1.3: The Summary and Linear Model with MCMC Multiple Imputation of Change from Baseline in Schirmer Test (mm) on Non-Study Eye at Visit 7 (Week 12) and other Post-Baseline Visits mITT
- Table 14.2.1.1.4: The Summary and Linear Model with MCMC Multiple Imputation of Change from Baseline in Schirmer Test (mm) on Non-Study Eye at Visit 7 (Week 12) and other Post-Baseline Visits PP

Sponsor:	Ocular Therapeutix, Inc.		
Protocol:	CLN-Protocol-0054		
Document Version No.:	V1.0	Document Date:	01-OCT-2021

- Table 14.2.2.1.1: The Summary and Linear Model with Last Observation Carried Forward (LOCF) of Change from Baseline in Schirmer Test (mm) on Study Eye at Visit 7 (Week 12) and other Post-Baseline Visits mITT
- Table 14.2.2.1.2: The Summary and Linear Model with Last Observation Carried Forward (LOCF) of Change fromBaseline in Schirmer Test (mm) on Study Eye at Visit 7 (Week 12) and other Post-Baseline Visits PP

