7.2. Data Listings to be Generated

- -Listing 16.1.1.1: Subject Disposition All Subjects Screened
- Listing 16.1.1.2: Eligibility All Subjects
- Listing 16.1.1.3: Major Protocol Deviations All Subjects Randomized

Listing 16.1.1.4: Subjects Excluded from the Efficacy Analysis – All Subject Randomized

Cytel

Statistical Analysis Plan

Sponsor:	Ocular Therapeutix, Inc.		
Protocol:	CLN-Protocol-0054		
Document Version No.:	V1.0	Document Date:	01-OCT-2021

Listing 16.1.2: Demographic and Baseline Characteristics - mITT and Cohort 1

- Listing 16.1.3.1: Ocular Medical History mITT and Cohort 1
- Listing 16.1.3.2: Non-Ocular Medical History mITT and Cohort 1
- Listing 16.1.4: Treatment Exposure SAFETY
- Listing 16.1.5: Schirmer's Test without Anesthesia Result- mITT and Cohort 1
- Listing 16.1.6: CFS Assessment mITT and Cohort 1
- Listing 16.1.7: CLGS Assessment mITT and Cohort 1
- Listing 16.1.8: VAS of Eye Dryness Score mITT and Cohort 1
- Listing 16.1.9: Ocular Surface Disease Index questionnaire (OSDI©) mITT and Cohort 1
- Listing 16.1.10: Standardized Patient Evaluation of Eye Dryness (SPEED) mITT and Cohort 1
- Listing 16.1.11: Tear Film Break Up Time (TBUT) mITT and Cohort 1
- Listing 16.1.12: Insert Placement at Visit 2 or Visit 2B mITT and Cohort 1
- Listing 16.1.13: Ease of insertion at Visit 2 or Visit 2B as assessed by the Investigator mITT and Cohort 1
- Listing 16.1.14: Presence of OTX-CSI or HV by Visual Assessment mITT and Cohort 1
- Listing 16.1.15: Ease of visualization as assessed by the Investigator mITT and Cohort 1
- Listing 16.1.16.1: All Adverse Events SAFETY
- Listing 16.1.16.2: Serious Adverse Events SAFETY
- Listing 16.1.16.3: Adverse Events leading to Discontinuation of Treatment SAFETY
- Listing 16.1.16.4: Subject Deaths SAFETY
- Listing 16.1.17: Best Corrected Visual Acuity (BCVA) SAFETY
- Listing 16.1.18: Slit-lamp Biomicroscopy and External Eye Exam SAFETY
- Listing 16.1.19: Intraocular Pressure (IOP) Measurement SAFETY
- Listing 16.1.20: Fundus Examination SAFETY

Listing 16.1.21: Use of Artificial Tears - SAFETY

Cytel

Statistical Analysis Plan

Sponsor:	Ocular Therapeutix, Inc.		
Protocol:	CLN-Protocol-0054		
Document Version No.:	V1.0 Document Date: 01-OCT-2021		

Listing 16.1.22: Urine Pregnancy Test - SAFETY

Listing 16.1.23: Concomitant Medications - SAFETY

Listing 16.1.24: Prior Medications - SAFETY

Sponsor:	Ocular Therapeutix, Inc.		
Protocol:	CLN-Protocol-0054		

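### The partial-date rule for medications defaults to prior when on-treatment use cannot be ruled out, the reverse of the SAP's adverse event rule and at odds with its own definition of concomitant

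*SAP*

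**What the plan says.** SAP 4.9.3 (Concomitant Medications) defines concomitant medications as "those medications that were initiated after study drug administration or those that were ongoing at the time of study drug administration". For a start or stop date that is partly missing, it asks for a comparison with the study drug date using whatever date parts are known. It then gives this default for such a drug: "assumed to be prior medication if it cannot be definitively shown that the medication did not start or continue during the treatment period". Completely missing dates are not mentioned, and the section does not define prior medication.

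SAP 4.2.9 sets the corresponding rule for adverse events with a partly or completely missing start date. After the same kind of comparison, the event is "assumed to be treatment-emergent if it cannot be definitively shown that the AE did not occur or worsen" in the treatment-emergent period, and the SAP labels this a worst-case approach. The detailed rules follow that direction. For a missing day, for example, "an AE will only be excluded as being treatment-emergent if the start month/year is before the month/year of study drug administration". An event that resolved before study drug is also excluded.

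SAP section 5 (Changes to Planned Analyses) does not mention the difference. The protocol has no partial-date rule for medications.

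**The concern.** Both rules turn on the same question: can the known date parts rule out the treatment period? For adverse events, an unresolved answer leads to the on-treatment class. For medications it leads to the off-treatment class. No reason is given for the reversal.

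The medication sentence also sits badly with the definition before it. The known date parts may already prove that a drug was started after insertion. It then plainly cannot be shown that the drug did not start during treatment, so the sentence, as worded, sends it to prior.

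What is at stake is the split between Tables 14.1.7.1 to 14.1.7.3 (prior) and 14.1.7.4 to 14.1.7.6 (concomitant, for example "Table 14.1.7.6: Non-ocular Concomitant Medications SAFETY"), and between Listing 16.1.24 and "Listing 16.1.23: Concomitant Medications - SAFETY". A programmer who codes the sentence as written would move on-treatment use out of the concomitant outputs if each record receives only one class.

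**Working it through.** The plan gives no figure to reproduce, so the check applies each rule to example records.

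**Inputs**
- Definition of concomitant and partial-date rule: SAP 4.9.3.
- Adverse event default: SAP 4.2.9.
- Assumed for illustration: insertion on 15 March 2021, and a drug counts as on treatment if its stop date is on or after that day.

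**Method.** For each record, list every calendar date (or start and stop pair with stop not before start) that fits the known parts, and count those on treatment. The SAP 4.9.3 sentence gives prior unless that count is zero. A rule in the adverse event direction gives concomitant unless that count is zero.

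**Counts**
- A. Start April 2021 (day missing), ongoing: every possible start is after insertion, so 30 of 30.
- B. Start 10 January 2021, stop March 2021 (day missing): stops on 15 to 31 March, 31 − 14 = 17, so 17 of 31.
- C. Start and stop both March 2021 (days missing): possible pairs 31 × 32 / 2 = 496; pairs ending by 14 March 14 × 15 / 2 = 105; on treatment 496 − 105 = 391, so 391 of 496.
- D. Start 10 January 2021, stop February 2021 (day missing): every possible stop is before insertion, so 0 of 28.

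| Record | On treatment | Definition alone | SAP 4.9.3 sentence | Adverse event direction |
|---|---|---|---|---|
| A | 30/30 | concomitant | prior | concomitant |
| B | 17/31 | undetermined | prior | concomitant |
| C | 391/496 | undetermined | prior | concomitant |
| D | 0/28 | not concomitant | not triggered | not concomitant |

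**Reading the table**
- A is a direct contradiction: concomitant by the definition, prior by the sentence.
- B and C do not contradict the definition, which cannot decide them. They receive the opposite default to the adverse event rule. An adverse event dated like C would be treatment-emergent.
- D is the one record that certainly ended before insertion, and it is the only one that the prior assumption does not reach.

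The counts show how the rule behaves. They are not probabilities or expected error rates.

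**The case against.** The strongest reply is that the sentence is only a fallback. SAP 4.9.3 first asks for a comparison of the known date parts with the study drug date. In record A the month alone settles that comparison, so A would never reach the assumption. This reading is possible, but the text contains no such exception. SAP 4.2.9 has the same two steps, and there the assumption sentence is the decision rule. Even as a fallback, the sentence still sends B and C to prior.

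A second reply is that nothing obliges medications and adverse events to share a default, since the worst-case label is attached to adverse events only. That is fair. For unresolved dates the rule is an unexplained, non-conservative choice, and the strict contradiction is confined to records that are certainly on treatment.

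Third, the harm is conditional. The SAP does not say that prior and concomitant are mutually exclusive, and separate tables do not prove it. If a drug may be counted in both, the concomitant tables lose nothing. This stands.

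The wording may be a slip, with prior written where concomitant was meant. That is an inference, and if it is right the sentence needs the same correction. If instead the double negative is the slip, and the intent was prior unless on-treatment use is shown, A is classed correctly but B and C still default to prior.

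**Conclusion.** The point holds, as a minor one. As written, the SAP 4.9.3 sentence misclassifies partial-date drugs that are certainly on treatment. On any reading that keeps the word prior, it also defaults unresolved dates away from concomitant.

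The possible effect is an understatement of concomitant use in Tables 14.1.7.4 to 14.1.7.6 and Listing 16.1.23. It depends on the two classes being exclusive and on partial-date records existing. Their number is not known and may be small or zero.

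The reach is limited to descriptive safety outputs:
- SAP 4.9.3 states that "All prior and concomitant medications information will be presented in the data listing", so no record is lost.
- Artificial tears have their own summary under SAP 4.9: "The use of artificial tears, based on the Daily Subject Diary, since last visit will be tabulated for each post-baseline visit".
- No efficacy model, imputation step or stated per-protocol criterion (SAP 3.1, 4.2.9.1 and 4.7) uses the classification.

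Confidence is high for the wording defect. Its practical effect in this trial cannot be judged from the documents.

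**What to change.** Replace the sentence in SAP 4.9.3 with:

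*If a start or stop date is partially or completely missing, the medication will be assumed concomitant unless the available date parts show that it stopped before study drug administration.*

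Under this wording A, B and C become concomitant and D does not. It also covers completely missing dates, which the adverse event rule addresses and the medication rule omits.

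Add one sentence stating whether a drug started before insertion and continued after it is counted as prior, concomitant or both. That settles whether the two sets of tables may overlap.

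The cost is one sentence replaced, one added and one derivation condition. No new data are needed and no efficacy output changes. If the tables have already been produced under another rule, the clinical study report should state the rule used, as protocol 11.9 requires for departures from the SAP.
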